| DOR | Duration of response |
| DSMC | Data safety monitoring committee |
| ECOG | Eastern Cooperative Oncology Group |
| EBV | Epstein Barr Virus |
| ES-SCLC | Extensive stage small cell lung cancer |
| EOTV | End of treatment visit |
| FFPE | Formalin fixed paraffin-embedded |
| GCP | Good clinical practice |
| HIPAA | Health Insurance Portability and Accountability |
| HTSR | Histopathology & Tissue Shared Resource |
| IB | Investigator's brochure |
| ICF | Informed consent form |
| IMP | Investigational medicinal product |
| IRB | Institutional review board |
| IRR | Infusion related reaction |
| LCCC | Lombardi comprehensive cancer center |
| LPLV | Last patient, last visit |
| mCRPC | Metastatic castration resistant prostate cancer |
| MGUH | MedStar Georgetown University Hospital |
| mIg | Membrane bound immunoglobulin |
| MRI | Magnetic resonance imaging |

| | |
|--------|---|
| NGS | Next generation sequencing |
| NSCLC | Non-small cell lung cancer |
| ORR | Objective response rate |
| OS | Overall survival |
| PD-1 | Programmed cell death 1 |
| PD-L1 | Programmed cell death ligand 1 |
| PET | Positron emission tomography |
| PFS | Progression free survival |
| PI | Principal investigator |
| PK | Pharmacokinetic |
| RECIST | Response evaluation criteria in solid tumors |
| SAE | Severe adverse event |
| SBRT | Stereotactic body radiation therapy |
| SCLC | Small cell lung cancer |
| SRS | Stereotactic radiosurgery |
| STIAMP | Suspected transmission of an infectious agent by the study drug |
| T3 | Free triiodothyronine |
| T4 | Free thyroxine |
| TcR | T-cell antigen receptor |
| TSH | Thyroid-stimulating hormone |
| ULN | Upper limit of normal |
| VAF | Variant allele frequency |
| WGS | Whole genome sequencing |
| WES | Whole exome sequencing |
| WTS | Whole transcriptome sequencing |

1. BACKGROUND

1.1 BACKGROUND ON SMALL CELL LUNG CANCER (SCLC)

Small cell lung cancer (SCLC) an exceptionally aggressive subtype of lung cancer; it accounts for 10-15% of all lung cancers (Gazdar et al. 2017). SCLC is characterized by early metastases along with rapid growth and resistance to treatment. In 2018, there was an estimated 29,514 new cases of SCLC with a 5-year survival rate of just 6.9%. About 75% of patients with newly diagnosed SCLC present with disseminated disease, with a 5-year survival of only about 3% (Surveillance Research Program, National Cancer Institute).

1.2 BACKGROUND ON THE TREATMENT OF EXTENSIVE STAGE SMALL CELL LUNG CANCER (ES-SCLC)

For extensive stage small cell lung cancer (ES-SCLC), the standard of care frontline treatment has generally involved platinum-based chemotherapy with etoposide for several decades. Despite high initial response rates of about 65%, patients will predictably experience relapse after chemotherapy alone, with median overall survival (OS) of only about 10 months (Rossi et al. 2012). In the last several years, immunotherapy has demonstrated clinical activity in ES-SCLC. The phase III IMpower133 trial demonstrated that in patients with ES-SCLC, the addition of atezolizumab to standard first-line platinum-based chemotherapy improved both PFS (5.2 months vs 4.3 months) and OS (12.9 months vs 10.3 months) when compared to platinum-based chemotherapy alone (Horn et al. 2018). The CASPIAN trial showed similar modest improvements in OS with the addition of the programmed cell death ligand-1 (PD-L1) inhibitor durvalumab to platinum-based chemotherapy (Paz-Ares et al. 2019).

Despite these improvements in therapy, the majority of patients will relapse. Outcomes in patients with relapsed or refractory ES-SCLC remain poor, with median OS of less than six months. Camptothecins such as topotecan are used as second-line therapy, however objective response rates (ORRs) are low at about 15% (Garst et al. 2007). The alkylating agent lurbinectedin obtained accelerated FDA approval in 2020 for patients with ES-SCLC who had disease progression on or after platinum-based chemotherapy. The overall response rate was 33% with median duration of response (DOR) of 5.1 months (Trigo et al. 2020). For patients with chemotherapy free interval ≥ 90 days, the response rates were even greater with ORR of 45% and median PFS of 4.5 months. In patients with chemotherapy free interval < 90 days, the ORR was 22% and median PFS of 2.6 months. Despite these recent advances, outcomes remain poor, and there is need to develop novel therapeutics for relapsed or refractory ES-SCLC.

1.3 BACKGROUND ON B7-H3

B7 homolog 3 protein (B7-H3), which is also known as CD276, is a type I transmembrane protein encoded on chromosome 15 and is a member of the B7 family of immune check points (Seaman et al. 2017). The B7 family of cell surface molecules consist of structurally related protein ligands that bind to receptors on lymphocytes and regulate immune responses. Activation of T and B lymphocytes is initiated by engagement of antigen-specific receptors, T cell antigen receptor (TcR) and membrane bound immunoglobulin (mIg) respectively, but additional signals delivered simultaneously to members of the CD28 family of receptors by B7 ligands determine the ultimate immune response (Collins et al. 2005). The B7-H3 pathway is involved in the immune response in various ways, including blocking NK mediated lysis and augmenting proinflammatory cytokines. Although B7-H3 mRNA is widely distributed, B7-H3 protein expression in normal human tissue is limited, presumably thought to be from the negative regulation of B7-H3 protein expression by the microRNA miR-29 (Xu et al. 2009). B7-H3 has been implicated in the delivery of both co-stimulatory and co-inhibitory signals (Hofmeyer et al. 2008).

B7-H3 is an appealing therapeutic target due to its overexpression in many malignant tumors and limited expression in normal tissues (Figure 1). Additionally, B7-H3 upregulation is associated with a worse prognosis.

Figure 1. Summary of B7-H3 expression in human cancer

| Potential Indications: | IHC Summary of >1,400 Tumor Tissue Samples Screened | | | |
|------------------------|---|------|-------------|------|
| | B7-H3 Positive ^(a) | | 2+ or Above | |
| Head and Neck | 19/19 | 100% | 19/19 | 100% |
| Kidney Cancer | 77/78 | 99% | 75/78 | 96% |
| Glioblastoma | 65/66 | 98% | 63/66 | 95% |
| Thyroid Cancer | 34/35 | 97% | 33/35 | 94% |
| Mesothelioma | 41/44 | 93% | 39/44 | 89% |
| Melanoma | 132/146 | 90% | 94/146 | 64% |
| Prostate Cancer | 88/99 | 89% | 51/99 | 52% |
| Pancreas Cancer | 69/78 | 88% | 45/78 | 58% |
| Bladder | 134/156 | 86% | 123/156 | 79% |
| Lung Cancer | 324/379 | 85% | 300/379 | 79% |
| Breast Cancer | 189/249 | 76% | 156/249 | 63% |
| Ovarian Cancer | 59/79 | 75% | 36/79 | 46% |

1.4 BACKGROUND ON VOBAMITAMAB DUOCARMAZINE (MGC018)

[figure not shown]

Figure 2. Schematic representation of MGC018 and mechanisms of release of prodrug from MGC018 and conversion to the active duocarmycin drug DUBA

[figure not shown]
1.5 STUDY RATIONALE AND BENEFIT-RISK ASSESSMENT

1.5.1 Study rationale for MGC018 in ES-SCLC with progression after prior platinum-based chemotherapy

[illegible][illegible]

| | 2019 | |
|--------------------|------|------|
| | 2019 | 2019 |
| 1. Total | 100 | 100 |
| 2. Government | 45 | 45 |
| 3. Private | 55 | 55 |
| 4. Non-profit | 10 | 10 |
| 5. For-profit | 45 | 45 |
| 6. Not-for-profit | 10 | 10 |
| 7. For-profit | 45 | 45 |
| 8. Not-for-profit | 10 | 10 |
| 9. For-profit | 45 | 45 |
| 10. Not-for-profit | 10 | 10 |
| 11. For-profit | 45 | 45 |
| 12. Not-for-profit | 10 | 10 |
| 13. For-profit | 45 | 45 |
| 14. Not-for-profit | 10 | 10 |
| 15. For-profit | 45 | 45 |
| 16. Not-for-profit | 10 | 10 |
| 17. For-profit | 45 | 45 |
| 18. Not-for-profit | 10 | 10 |
| 19. For-profit | 45 | 45 |
| 20. Not-for-profit | 10 | 10 |

2. OBJECTIVES AND ENDPOINTS

2.1 PRIMARY OBJECTIVE

- To determine the efficacy of MGC018 in patients with relapsed or refractory ES-SCLC as defined by investigator-assessed ORR according to RECIST v1.1

2.2 SECONDARY OBJECTIVES

- To evaluate the safety profile of MGC018 in patients with relapsed or refractory ES-SCLC
- To examine duration of response (DOR), progression-free survival (median PFS and 6-month PFS), and overall survival

2.3 EXPLORATORY OBJECTIVES

- To assess efficacy of MGC018 according to the expression of B7-H3 on tumor tissue
- To assess the role of blood-based biomarkers in predicting response and resistance to MGC018

3. STUDY DESIGN

3.1 DESCRIPTION OF THE STUDY

[figure not shown]
3.1.1 Study schema & overview of study design

This is an open label phase 2, multi-center, single arm study evaluating the efficacy of MGC018 in patients with relapsed or refractory ES-SCLC. Our cohort will enroll patients with ES-SCLC who experience progression during or following treatment with platinum-based chemotherapy. For full detailed inclusion/exclusion criteria, see section 4.1.

Patients enrolled will receive MGC018 at 2.0 mg/kg every 28 days continuously until completion of 8 cycles, disease progression, or unacceptable toxicity. Tumor assessment will be done every 2 cycles. The primary endpoint of the study will be assessed by ORR utilizing RECIST v1.1.

Key secondary endpoints will include incidence of adverse events per CTCAE v5.0, DOR, PFS, and OS. In an exploratory fashion, we plan to evaluate efficacy according to expression of B7-H3 on tumor tissue and blood-based biomarkers. Pre-treatment biopsy will be obtained to assess expression of B7-H3 on tumor tissue. If biopsy is not considered safe and medically feasible by the investigator, the patient may be approved for enrollment after consultation the principal investigator. In this case, we will obtain archival tissue if available. Expression of B7-H3 and other immune markers on tumor tissue will be assess using Imaging Mass Cytometry (Fluidigm platform) and correlated with treatment outcomes such as ORR, PFS, and OS. Blood samples will be obtained for biomarker analysis at day 1 of cycle 1, on day 1 of cycle 3, and at time of progression.

Figure 3 – Study Schema (N=17)

3.1.2 Hypothesis

Administration of MGC018 will achieve a clinically meaningful response rate of 25% in patients with relapsed or refractory ES-SCLC.

3.1.3 Summary of sample size calculation, study accrual and duration

Using the Simon's optimal two-stage design (Simon, Controlled clinical trials, 1989), we plan to enroll up to 17 patients. The null hypothesis that the true response rate is 5% will be tested against a one-sided alternative. In the first stage, 9 patients will be accrued. If there is no response in these 9 patients, the study will be stopped. If there is at least one response (including unconfirmed partial response) in the first 9 patients, 8 additional patients will be accrued for a total of 17. The null hypothesis will be rejected if 3 or more responses are observed in 17 patients. This design yields a type I error rate of 4.7% and power of 81.2%, when the true response rate is 25%. Time-to-event data, such as DOR, PFS, and OS, will be estimated using the Kaplan-Meier method. Cox proportional hazards models will be used to estimate hazard ratios. Safety data will be summarized descriptively. Adverse events will be summarized by severity, seriousness, and relationship to the study drug.

Patients will be enrolled at Georgetown Lombardi Comprehensive Cancer Center (LCCC), Washington Hospital Center, John Theurer Cancer Center, and Rutgers Cancer Institute of New Jersey at University Hospital. Other sites may be added to the study. Combined expected accrual is 1-2 patients per month. With expected required accrual period of 12 months duration. Patients will be followed with imaging tumor assessments every 2 cycles assess ORR. Upon progressive disease or unacceptable toxicity, patients will be taken off study and monitored every 6 months for two years for survival data.

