4.2.3.2 Guidelines for management of suspected MGC018-related toxicities

Criteria for treatment modification and guidelines for the management of toxicities are summarized below. Generally, temporary suspension of MGC018 must occur if a patient experiences a serious adverse event or a grade 3 or 4 non-serious adverse event assessed by the investigator as related to MGC018. If the event resolves to grade ≤ 1 , MGC018 may be restarted at the same dose level. If MGC018 is delayed due to toxicity for > 8 weeks beyond when the next dose should have been given, the patient must be permanently discontinued from MGC018.

PULMONARY EVENTS

Immune-mediated pulmonary events are a potential risk with MGC018. Patients will be assessed for pulmonary signs and symptoms throughout the study and will have computed tomography (CT) scans of the chest performed at every tumor assessment.

All pulmonary events should be thoroughly evaluated for other commonly reported etiologies such as pneumonia or other infection, lymphangitic carcinomatosis, pulmonary embolism, heart failure, chronic obstructive pulmonary disease, or pulmonary hypertension. Management guidelines for pulmonary events are provided in Table 5.

Table 5. Management Guidelines for Pneumonitis

| Event | Management |
|--------------|---|
| Grade 1 | 
 • Continue MGC018 and monitor closely. • Re-evaluate on serial imaging. • No specific therapy required |
| Grade 2 | 
 • Hold MGC018 • Consider treatment with corticosteroids equivalent to 1–2 mg/kg/day oral prednisone or equivalent divided twice daily • Taper corticosteroids over 4 weeks or as clinically indicated • Resume MGC018 administration at next scheduled dose if pneumonitis resolves to grade 1 or baseline within 5 days with or without treatment. On resuming MGC018, reduce dose by one dose level. • Discontinue MGC018 after second occurrence |
| Grade 3 or 4 | 
 • Permanently discontinue MGC018 • Hospitalize • Referral for pulmonary consult with diagnostic evaluation with chest X-ray and CT scan. • Initiate treatment with IV corticosteroids, suggest methylprednisolone at 2 to 4 mg/kg/day divided twice daily. Higher doses may be used in consultation with the sponsor's medical monitor. • If event does not improve within 3 to 5 days after initiating corticosteroids, consider adding an immunomodulatory agent. |

HEPATIC EVENTS

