4.3.1 Prohibited therapy

Use of the following concomitant therapies is prohibited as described below:

- Concomitant therapy intended for the treatment of cancer (including, but not limited to, chemotherapy, hormonal therapy, immunotherapy, radiotherapy, and herbal therapy), whether health authority–approved or experimental, is prohibited during study treatment, until disease progression is documented and the patient has discontinued study treatment.
- Live, attenuated vaccines (e.g., FluMist®) are prohibited within 4 weeks prior to initiation of study treatment, during study treatment, and for 5 months after the last dose of study treatment.

- Available vaccines for COVID-19 will be permitted at any time while a patient is enrolled on study but preferably not administered on same day as study drug infusion to avoid potential for overlapping immune-related reactions.

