4.4.5 Tumor response evaluations

Any evaluable or measurable disease must be documented at screening and re-assessed at each subsequent tumor evaluation. Tumor assessments performed as standard of care prior to obtaining informed consent and within 28 days prior to initiation of study treatment do not have to be repeated at screening. Measurable disease is a requirement for study inclusion and response will be assessed by the investigator per RECIST v1.1 at baseline. Patients will undergo tumor assessments every 2 cycles while on study until radiographic disease progression per RECIST v1.1 or loss of clinical benefit as determined by the investigator. Tumor assessments should be performed during the last week of the cycle and before the start of treatment in the next cycle (see Appendix 1). At the investigator's discretion, tumor assessments may be repeated at any time if progressive disease is suspected.

Screening assessments must include CT or magnetic resonance imaging (MRI) scans (with IV contrast unless contraindicated) of the chest, abdomen, and pelvis. If a positron emission tomography (PET)/CT scan is performed, the CT portion of the study must be consistent with the standards of a full-contrast diagnostic CT scan unless IV contrast is contraindicated. A CT scan with contrast or MRI scan of the head must be done at screening to evaluate for the presence of CNS metastases in all patients (MRI preferred). An MRI scan of the head is required to confirm or refute the diagnosis of CNS metastases at baseline in the event of an equivocal CT scan. At the investigator's discretion, other methods of assessment of measurable disease as per RECIST v1.1 may be used.

All measurable and evaluable lesions identified at baseline should be re-assessed at each subsequent tumor evaluation. The same radiographic procedures used to assess disease sites at screening should be used for subsequent tumor assessments (e.g., the same contrast protocol for CT scans). Stable brain metastases must be evaluated with each subsequent tumor assessment with the same radiographic procedure as the baseline study. Patients without brain metastases do not need brain scans for subsequent on-treatment tumor assessment unless clinically warranted or part of standard-of-care treatment.

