4.5 TREATMENT, PATIENT, AND STUDY DISCONTINUATION

4.5.1 Treatment discontinuation

Patients must permanently discontinue study treatment if they experience any of the following:

- Intolerable toxicity related to study treatment, determined by the investigator to be unacceptable given the individual patient's potential response to therapy and severity of the event
- Any medical condition that may jeopardize the patient's safety if he or she continues study treatment
- Investigator determines it is in the best interest of the patient
- Use of another non-protocol anti-cancer therapy
- Pregnancy

- Loss of clinical benefit as determined by the investigator after an integrated assessment of radiographic and biochemical data, local biopsy results (if available), and clinical status (e.g., symptomatic deterioration such as pain secondary to disease)
- Radiographic disease progression per RECIST v1.1 or symptomatic deterioration attributed to disease progression

In select scenarios, patients may continue therapy in setting of radiographic progression and ongoing clinical benefit, as assessed by investigator. In this scenario, medical interventions such as stereotactic radiosurgery (SRS) and stereotactic body radiation therapy (SBRT) to isolated sites of disease progression in the setting of otherwise ongoing treatment response will be allowed on a case-by-case basis with PI approval.

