The primary reason for study treatment discontinuation should be documented in the patient's medical records and on the appropriate eCRF. Patients who have received ≥ 1 cycle of study therapy and discontinue study treatment prematurely will not be replaced. Patients will return to the clinic for a treatment discontinuation visit ≤ 30 days after the last dose of study treatment. The visit at which response assessment shows progressive disease may be used as the treatment discontinuation visit. After the end of treatment visit, all adverse events (including serious adverse events [see Section 5.2.2], regardless of attribution, will be recorded until 60 days after the last dose of study treatment or until initiation of another anti-cancer therapy, whichever occurs first. Protocol-defined events of special interest [see Section 5.2.3]) will be recorded until 60 days after the last dose of study treatment regardless of whether or not subsequent anti-cancer therapy is initiated. Ongoing adverse events thought to be related to study treatment will be followed until the event has resolved to baseline grade, the event is assessed by the investigator as stable, new anti-tumor treatment is initiated, the patient is lost to follow up, the patient withdraws consent, or it has been determined that the study treatment or participation is not the cause of the adverse event.

Patients who discontinue study treatment for any reason other than progressive disease or loss of clinical benefit will continue to undergo tumor response assessments as outlined in the schedule of activities (see Appendix 1).

After treatment discontinuation, information on survival follow-up and new anti-cancer therapy will be collected via telephone calls, patient medical records, and/or clinic visits approximately every 6 months for 2 years (unless the patient withdraws consent or the PI terminates the study).

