6.3 SECONDARY EFFICACY VARIABLES

Secondary efficacy variables include:

- PFS: Defined as the time from study drug initiation until progression event or death as assessed using the Kaplan-Meier method.
- OS: Defined as time from study drug initiation to death as assessed using the Kaplan-Meier method.
- DOR: Defined as the time from response to disease progression or death in patients who achieve complete or partial response.

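### Scan timing moves with dose delays, follow-up after a toxicity stop is contradictory, and the PFS and DOR event and censoring rules are unstated, which puts 6-month PFS at risk

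*Combined protocol and SAP*

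**What the plan says.** **Scan schedule.** Section 3.1.1: "Tumor assessment will be done every 2 cycles". Section 4.4.5 places the scan in the last week of a cycle, before the next dose. Appendix 1, Table 2, footnote d gives a window of 7 days before the next scheduled treatment. No date counted from first dose is given. Section 4.2.3.2 permits a toxicity delay of up to "8 weeks beyond when the next dose should have been given"; several of the event tables set 21 or 28 days. Under section 4.4, a postponed dose restarts the 28-day count unless the slip is under 3 days. Treatment ends after cycle 8.

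**When scans stop.** Section 4.4.5: "Patients will undergo tumor assessments every 2 cycles while on study until radiographic disease progression per RECIST v1.1 or loss of clinical benefit". Section 4.5.1: "Patients who discontinue study treatment for any reason other than progressive disease or loss of clinical benefit will continue to undergo tumor response assessments". Footnote d agrees with 4.5.1. Section 3.1.3 differs: "Upon progressive disease or unacceptable toxicity, patients will be taken off study and monitored every 6 months for two years for survival data".

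**Endpoints.** Section 2.2 names median and 6-month PFS as secondary. Section 6.3: "PFS: Defined as the time from study drug initiation until progression event or death as assessed using the Kaplan-Meier method". DOR runs from response to progression or death. Neither definition has a censoring rule, and what counts as a progression event is not defined.

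**Radiotherapy.** Section 4.3.1 says anticancer therapy, radiotherapy included, "is prohibited during study treatment, until disease progression is documented and the patient has discontinued study treatment". Section 4.5.1 says stereotactic treatment "to isolated sites of disease progression in the setting of otherwise ongoing treatment response will be allowed on a case-by-case basis with PI approval", in patients who stay on drug.

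**The concern.** Progression is recorded only when someone scans. If toxicity holds the dose, it also moves the scheduled scan, so the recorded PFS depends on tolerability as well as on disease. A patient who deteriorates without a RECIST scan leaves the scan schedule, and the plan leaves three treatments open: event at clinical failure, censoring at the last scan, or failure only at death. A site that follows section 3.1.3 could stop scanning a patient whom section 4.5.1 and Appendix 1 require it to scan.

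At stake is the reading of 6-month PFS and, by the same mechanism, DOR. With 17 patients each one is worth 1/17, or about 6 percentage points, so a few unresolved cases change the reported figure. The rules should be set before outcomes are known.

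**Working it through.** **The plan's own figure.** The documents give no figure for PFS or DOR. The stated operating characteristics are for ORR: stop at 0 of 9, reject at 3 or more of 17. The sum over x₁ = 1 to 9 of P(X₁ = x₁)·P(X₂ ≥ 3 − x₁), with X₁ ~ Bin(9, p) and X₂ ~ Bin(8, p), is 0.0466 at p = 0.05 and 0.8122 at p = 0.25. The stated 4.7% and 81.2% are reproduced. They depend only on the response rate and the boundaries, so this point does not alter them.

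**Inputs for PFS.**
- Scan interval: 2 × 28 days = 8 weeks.
- Six months = 26.1 weeks (4.348 weeks per month).
- True median m: 2.6 or 4.5 months, the lurbinectedin subgroup figures in section 1.2, used for illustration.
- Assumptions not in the documents: exponential PFS, S(t) = 2^(−t/m); the share of patients with a delay; the share censored.

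**Baseline: fixed 8-week scans, nobody lost.** The last scan before 6 months is at week 24 (5.52 months), so reported 6-month PFS equals S(24 weeks).
- m = 2.6: 2^(−5.52/2.6) = 0.230, against a true 0.202.
- m = 4.5: 2^(−5.52/4.5) = 0.427, against a true 0.397.

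Mean late-dating is 4.3 and 4.2 weeks, so some exists even on a perfect schedule.

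**Dose delays.** The third scan passes the 6-month landmark once cumulative delay exceeds 26.1 − 24 = 2.1 weeks, or 3.1 weeks if the 7-day window is used in full. Give each affected patient one delay, equally likely in the first, second or third scan interval.
- *3 weeks, all patients.* The last scan before 6 months is at week 19 (probability 2/3) or week 16 (1/3). m = 2.6: (2 × 0.312 + 0.375)/3 = 0.333. m = 4.5: (2 × 0.510 + 0.567)/3 = 0.529.
- *8 weeks, 30% of patients.* For those delayed, the last scan is at week 24 (2/3) or week 16 (1/3). m = 2.6: 0.7 × 0.230 + 0.3 × 0.278 = 0.244. m = 4.5: 0.7 × 0.427 + 0.3 × 0.474 = 0.441.

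These are the ends of the range: 24–33% and 44–53%. The 3-week delay does more here than the 8-week one, because an early 8-week slip puts the second scan at week 24, still before the landmark. In simulation (400,000 patients) mean late-dating rises to 4.5–6.4 weeks (m = 2.6) and 4.3–5.7 weeks (m = 4.5).

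**Loss of clinical benefit, if censored at the last scan.** Let s be true survival over one interval and q the share of progressors censored. The Kaplan-Meier factor per interval becomes s′ = s/[s + (1 − q)(1 − s)], and 6-month PFS is s′³.

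| m (months) | s | q = 0 | q = 0.1 | q = 0.2 | q = 0.3 |
|---|---|---|---|---|---|
| 2.6 | 0.612 | 23% | 26% | 29% | 33% |
| 4.5 | 0.753 | 43% | 46% | 50% | 54% |

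**Toxicity stop, if scans end there.** Simulated with 10–30% of patients stopped and a hazard after the stop of 1 to 2 times the hazard before. Censored 6-month PFS is 21–22% against 19–23% with follow-up (m = 2.6), and 41–42% against 37–43% (m = 4.5). The difference runs from −2 to +3 points.

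**Median.** It stays at the week-16 scan (3.7 months) in every case above for m = 2.6. For m = 4.5 it stays at the week-24 scan (5.5 months), except that it reaches 6.2–6.4 months when every patient has a 3- or 4-week delay and 7.4 months at q = 0.3.

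DOR was not simulated; its progression date is exposed in the same way.

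**The case against.** A reader might infer that the plan informatively censors PFS and so biases it upward. The documents do not go that far. No section says these patients are censored: the progression event could be taken to include clinical failure, and survival follow-up continues, so death would still count. What is established is a missing rule.

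Other limits also stand:
- Eight weeks is the outer limit for a delay; many event tables are tighter. Section 4.4.5 lets the investigator scan at any time if progression is suspected, which reduces late-dating but leaves it to discretion.
- The sentence in section 3.1.3 is a summary and does not mention scans, while section 4.5.1 and Appendix 1 agree with each other. It is a contradiction to remove, and the direction of any bias from it is unknown.
- After cycle 8, footnote d can be read as continuing the same interval. That is implied, not stated.
- A reader might expect that censoring a fifth of progressions inflates the median by 1/(1 − 0.2) = 1.25. That needs continuously observed progression. On the 8-week grid with q = 0.2 the median does not move (for m = 4.5 only just: the curve is at 0.497 at week 24).
- No PFS comparison with historical medians is planned; the figures in section 1.2 are background.
- With n = 17 the binomial standard error of 6-month PFS is √(0.23 × 0.77/17) = 10 points or √(0.43 × 0.57/17) = 12 points, so most of these shifts are below one standard error. A systematic shift still adds to that noise.
- Section 4.5.1 may be meant as an approved exception to section 4.3.1, but neither section refers to the other.

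**Conclusion.** The point holds as a risk to the secondary endpoints, chiefly 6-month PFS, and is worth correcting. Three things are firm from the text: scheduled scans move with doses, section 3.1.3 conflicts with section 4.5.1 and Appendix 1, and section 6.3 leaves events and censoring undefined although scanning stops at loss of clinical benefit. Over the delay and censoring shares examined, reported 6-month PFS rises by about 1 to 11 points above what a fixed 8-week schedule with complete follow-up would give. Those shares and the exponential form are assumptions, and unscheduled scans would shrink the delay effect. A definite upward bias, a general inflation of the median, or any effect on the ORR decision rule is not supported.

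**What to change.** 1. In sections 4.4.5 and 3.1.3 and in Appendix 1 footnote d, schedule scans every 8 weeks from first dose with a fixed window, regardless of dose delays and after treatment ends (including after cycle 8), until RECIST progression, death or withdrawal.
2. Reconcile the off-study sentence in section 3.1.3 with section 4.5.1 and Appendix 1, so that scans continue after a stop for toxicity.
3. In section 6.3, define the PFS and DOR event as first RECIST progression or death. State the censoring rules, including the one for new anticancer therapy. Add a sensitivity analysis that counts loss of clinical benefit attributed to disease as an event. State that the first RECIST progression date stands if treatment continues.
4. Reconcile sections 4.3.1 and 4.5.1 on radiotherapy during treatment.

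The cost is mostly wording. The nominal 8-week interval is unchanged, and section 4.5.1 already requires scans after a toxicity stop. The new burden is scanning after clinical failure, where feasible. Reported PFS may come out slightly shorter. A fixed schedule still dates progression about 4 weeks late on average, but no longer in a way that depends on dosing.
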